2.0 Abbreviations

ACR	American College of Rheumatology
AE	Adverse Events
ANOVA	Analysis of Variance
CRF	Case Report Form
CRP	C-Reactive Protein
CTCAE	Common Terminology Criteria for Adverse Events
DAS28	Disease Activity Score in 28 Joints
EQ-5D-3L	EuroQol 5 dimension, 3 level quality of life questionnaire
ESR	Erythrocyte Sedimentation Rate
EULAR	The European League Against Rheumatism
GP	General Practitioner
HAQ DI	Health Assessment Questionnaire Disability Index
HCRU	Healthcare Resource Utilization
ICF	Informed Consent Form
ICH-GCP	International Conference on Harmonization of Good Clinical Practice
NRS	Numeric Rating Scale
PGIC	Patient Global Impression of Change
PHI	Protected Health Information
PRO	Patient-Reported Outcome
QC	Quality Check
QoL	Quality of Life
RA	Rheumatoid Arthritis
SAP	Statistical Analysis Plan
SF-36	Short Form 36-Item Health Survey
SOC	System Organ Class
SOP	Standard Operating Procedure
TNF	Tumor Necrosis Factor
VAS	Visual Analogue Scale
WPAI	Work Productivity and Activity Impairment

4.0 Abstract

Title: Real-World Outcome of Adalimumab on Rheumatoid Arthritis Patients in Taiwan.

Rationale and Background: Given the requirement to keep a balance between effectiveness and cost containment to ensure that the available health resources are used in a cost-effective manner, there is an increasing demand for real-world evidence (RWE) from policy makers, regulators, providers and payers in the region to optimize spending and patient outcomes.

So far, there are no data available regarding adalimumab's impact on patients' quality of life (QoL) and healthcare resource utilization (HCRU) in a realistic study design, which provides greater generalization in Taiwan.

The goal of this study is to determine the QoL, HCRU and costs of the patients care in subjects with RA who are treated with adalimumab in these three countries.

Results from study on the impact of adalimumab on Work Productivity and Activity Impairment (WPAI) scores and other Patient-Reported Outcomes (PROs) will be of interest to a variety of stakeholders in the healthcare system including patients, healthcare practitioners and payers in Taiwan.

Research Question and Objectives: The objective of this non-interventional, observational study is to assess the impact of adalimumab on health-related QoL and work productivity in patients with Rheumatoid Arthritis (RA) in Taiwan. Specifically, to achieve the above objective the following concrete steps will be taken:

1. Recruit investigators who are willing and able to recruit and follow new adalimumab users for 6 months follow-up
2. Collect the patients' clinical profile, patient-reported QoL, functioning, work productivity, treatment satisfaction and HCRU of RA patients at adalimumab initiation
3. Follow the patients initiating adalimumab for 24 weeks and identify the changes in clinical, economic, and PROs associated with adalimumab

Study Design: The study is designed as a prospective, observational study to assess the effect of adalimumab on health-related QoL and work productivity in patients with RA in Taiwan.

Note: This study is non-interventional and the subjects/investigators will follow the current clinical practice in each site and also the routine clinical follow up as determine by the treating physician.

RA patients, for whom adalimumab treatment has already been decided, will be recruited from within the clinical settings of each rheumatologist participating in the study. Approximately 100 patients diagnosed with RA that meet the inclusion and exclusion criteria will be enrolled at approximately 7 sites in Taiwan.

To assess health and disability outcomes, the HAQ DI at baseline, Week 12 and Week 24 after treatment initiation with adalimumab will be collected. In addition, other PROs of work activity and well-being, including the WPAI, EQ-5D, and SF-36, will also be collected.

In addition, the health care resource utilization will be collected. This includes surgical procedures, hospitalizations, bed days in hospital, physician consultations etc. Costs will be assigned based on the health care resource utilization using standardized costs for each participating centers.

Population: Subjects will be males and/or females who are attending a routine clinical visit and meet all of the inclusion criteria and none of the exclusion criteria. Approximately 100 patients diagnosed with RA will be recruited.

Inclusion Criteria:

Patients meeting all of the following inclusion criteria at baseline will be included:

1. Subject has a diagnosis of RA as defined by the 1987 revised American College of Rheumatology (ACR) classification criteria and/or the ACR/the European League against Rheumatism (EULAR) 2010 classification criteria (any duration since diagnosis).
2. Male or female subjects ≥ 18 years of age (local definition according to adalimumab label) who is in compliance with eligibility for adalimumab based on the local label.
3. Patients with moderate to severe RA defined as Disease Activity Score in 28 Joints (DAS28) (ESR) or DAS28 (CRP) >3.2
4. Biologically treatment naïve and initiated adalimumab at baseline visit
5. Availability of clinical data of the previous 12 weeks prior to baseline
6. Ability to self-complete patient questionnaires
7. Subject must be able and willing to provide written informed consent and comply with the requirements of this study protocol.

Exclusion Criteria:

Patients meeting any of the following exclusion criteria at baseline will be excluded:

1. Patients who are pregnant or breast feeding at enrolment or wish to become pregnant in the next 24 weeks.
2. Participation in any RA-related clinical trial at the time of enrolment, at baseline or at any point during the past 24 weeks prior to baseline
3. Patients, who in the clinician's view, may not be able to accurately report their QoL or prior resource utilization
4. Patients, who in the clinician's view, may not be able to adhere to adalimumab therapy over 24 weeks.

Variables:

Primary Variable

- Change in HAQ DI score at week 24 from baseline

Secondary Variable

- Change in other PROs (SF-36 domain scales, EQ-5D Index, Work Productivity and Activity Impairment Questionnaire [WPAI]) from baseline to weeks 12 and 24
- Change in HAQ DI score at week 12 from baseline
- Number and percent of patients achieving a clinically meaningful improvement on the HAQ DI, from baseline to weeks 12 and 24
- Healthcare Resource Utilization (HCRU) at baseline, 12 and 24 weeks

Exploratory Variable

- Difference of the change in HAQ DI score from baseline to 24 weeks between as observed population and withdrawal population
- Change in patient satisfaction questions from baseline to weeks 12 and 24
- Patient's impression of change at weeks 12 and 24 from baseline
- Association between disease severity and PROs
- Association between change in disease severity and change in PROs

Data Sources: Case Report Forms (CRFs) and patient questionnaires. Collection of data includes but not limited to subject demographics, clinical history, comorbidities, spontaneous adverse events, and concomitant medications. The following questionnaires will be utilized to collect data directly from participating subjects:

- EQ-5D
- SF-36
- HAQ DI
- WPAI
- HCRU
- Patient Global Impression of Change (PGIC)
- Patient Treatment Satisfaction Questions

Study Size: Approximately 100 patients diagnosed with RA will be recruited. The planned sample size provides at least 95% power for detecting a statistically significant improvement in HAQ-DI (Δ HAQ-DI < 0) assuming a mean Δ HAQ-DI of -0.21 and a standard deviation of 0.5 (reference 11), at two-sided significance level of 0.05 and accounting for a 10% dropout rate. The sample size also provides at least 95% power for detecting a statistically significant clinically meaningful improvement in HAQ-DI (Δ HAQ-DI < -0.22) assuming a mean Δ HAQ-DI of -0.5 and a standard deviation of 0.7, at two-sided significance level of 0.05 and accounting for a 10% dropout rate. For the secondary endpoint WPAI, the sample size provides 63% power for detecting a statistically significant improvement in "hours of work lost" at two-sided significance level of 0.05 and accounting

for a 10% dropout rate, assuming a mean change in “hours of work lost” of 10 and standard deviation of 30 and assuming a 55% employment rate in the study population.

Data Analysis:

Primary Endpoint Analysis

Change in HAQ DI score at 24 weeks after the initiation of adalimumab, in those patients continuing on adalimumab (as observed population). This change will be summarized as the mean and 95% confidence interval and will be tested with a paired t-test.

Secondary Endpoint Analysis

- Change in HAQ DI score at 12 weeks after the initiation of adalimumab, in those patients continuing on adalimumab (as observed population). This change will be summarized as the mean and 95% confidence interval and will be tested with a paired t-test.
- Change in other patient reported outcomes (SF-36 domain scales, EQ-5D Index, WPAI total lost productivity) at weeks 12 and 24 after the initiation of adalimumab, in those patients continuing on adalimumab (as observed population). These changes will be summarized as the means and 95% confidence intervals and will be tested with paired t-tests.
- Number and percent of patients achieving a clinically meaningful improvement on the HAQ DI, as defined by a -0.22 point improvement or greater, at weeks 12 and 24 after the initiation of adalimumab, in those patients continuing on adalimumab (as observed population).

Exploratory Endpoint Analysis

- Change in HAQ DI score at 24 weeks after the initiation of adalimumab, in those patients continuing on adalimumab (as observed population), compared with those patients not continuing on adalimumab (withdrawal population). The mean changes in these two groups will be compared using an independent t-test.
- Healthcare resource utilization will be described using number and percentage within each category (number of consultations, number of procedures received, number of surgeries, number of hospitalizations and length of stay, number of concomitant medications)
- Change in patient satisfaction questions at weeks 12 and 24 after the initiation of adalimumab, in those patients continuing on adalimumab (as observed population). These changes will be summarized as number and percentage of each response and compared with Kruskal-Wallis test. Satisfaction will also be dichotomized and analyzed over time with Cochrane-Armitage test for trends.
- Patient’s impression of change at weeks 12 and 24 after the initiation of adalimumab, in those patients continuing on adalimumab (as observed population). These changes will be summarized as number and percentage of each response and compared with Kruskal-Wallis test.
- Associations between disease severity and PROs
- Associations between change in disease severity and change in PROs

Milestones:

Start of Data Collection (FPFV):	10 October 2015
End of Data Collection:	31 January 2017
Database Lock:	28 February 2017
Interim Database Lock:	nil
Interim Report:	nil
Final Report of Study Results:	30 June 2017

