9.1.1 Schedule of Events

Table 1 Data Collection/Observation

	Data Collection/Observation	Baseline ^a ± 7 days	Week 12 (V2) ± 7 days	Week 24 (V3) ± 7 days	Early Termination / Drop out	70 days after the Week 24 or the last dose	150 days after the Week 24 or the last dose
Clinician Packet	Inclusion/exclusion form	X					
	Clinical history/patient demographics	X					
	Comorbidities	X					
	DAS28 (ESR) or DAS28 (CRP)	X	X	X	X		
Patient Packet	EuroQoL 5-Dimension (EQ-5D)	X	X	X	X		
	Short Form 36-Item Health Survey (SF-36)	X	X	X	X		
	Health Assessment Questionnaire (HAQ)	X	X	X	X		
	Work Productivity and Activity Impairment Questionnaire (WPAI)	X	X	X	X		
	Healthcare Resource Utilization (HCRU)	X	X	X	X		
	Patient Global Impression of Change (PGIC)		X	X	X		
	Patient Treatment Satisfaction Questions	X	X	X	X		
Clinicia	Adverse events	←				→	
	Pregnancy	←				→	

a. The Baseline will serve as the reference date for all subsequent time-points. A ± 7 day window is permitted around scheduled data collection time-points.

9.2

Setting

The study will take place in single country (Taiwan) with multiple centers. The study sites will be identified and selected by AbbVie. The study population shall comprise of male and/or female patients who are attending a routine clinical visit and meet all of the inclusion criteria and none of the exclusion criteria. Overall, approximately 100 subjects with clinically diagnosed RA are planned to be enrolled in the study at up to 7 sites.

The recruiting investigators will select potentially eligible patients from consecutive visits within their clinic based on the inclusion and exclusion criteria (Section 9.2.1 and Section 9.2.2). It is the responsibility of each physician to ask every consecutive patient who meets the inclusion criteria of the study to participate to avoid selection bias, and if investigators hold different types of clinics (e.g. routine visit clinics versus emergency clinics), only patients visiting their routine clinics will be used for patient selection.

Site personnel should thoroughly assess the eligibility criteria and evidence of this should be stored with the source documentation at site. Where there is any deviation from the inclusion/exclusion criteria, the patient should be excluded from the study.

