approximately 70 days after the Week 24 dosing or the last dose of adalimumab to determine the status of any ongoing AEs/SAEs or the occurrence of any new AEs/SAEs. The information will be recorded on the appropriate in eCRF page.

For subjects that are considered lost to follow-up, reasonable attempts must be made to obtain information on the final status of the subject. At a minimum, two phone calls must be made and one certified letter must be sent.

9.3 **Variables**

Variables (as observed):

Primary Variable

- Change in HAQ DI score at week 24 from baseline

Secondary Variable

- Change in other PROs (SF-36 domain scales, EQ-5D Index, Work Productivity and Activity Impairment Questionnaire [WPAI]) from baseline to weeks 12 and 24
- Change in HAQ DI score at week 12 from baseline
- Number and percent of patients achieving a clinically meaningful improvement on the HAQ DI, from baseline to weeks 12 and 24
- Healthcare Resource Utilization (HCRU) at baseline, 12 and 24 weeks

Exploratory Variable

- Difference of the change in HAQ DI score from baseline to 24 weeks between as observed population and withdrawal population
- Change in patient satisfaction questions from baseline to weeks 12 and 24
- Patient's impression of change at weeks 12 and 24 from baseline
- Association between disease severity and PROs
- Association between change in disease severity and change in PROs

9.4 **Data Sources**

Case Report Forms (CRFs) and patient questionnaires.

Collection of data includes but not limited to subject demographics, clinical history, comorbidities, spontaneous adverse events, and concomitant medications. The following questionnaires will be utilized to collect data directly from participating subjects:

- EQ-5D
- SF-36
- HAQ DI
- WPAI

- HCRU
- Patient Global Impression of Change (PGIC)
- Patient Treatment Satisfaction Questions

9.5 **Study Size**

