9.7.3 Planned Methods of Statistical Analysis

All statistical tests will be two-tailed with a significance level of 0.05. Descriptive statistics will be provided. Descriptive analysis will be conducted on all key parameters and presented as mean, standard deviation, minimum, maximum, and median when continuous and as "n" and percent when categorical. Change from adalimumab initiation to 24 weeks will be calculated and evaluated for significant improvements using paired t-tests / ANOVA for parametric and Wilcoxon signed-rank for non-parametric data. Analysis will be also be conducted by severity level (moderate vs severe), disease duration quartile (to compare to prior work) and up to two (2) other subgroups. Cochran-Armitage test of trends or other similar methods may be used to compare categories of subjects.

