3.5 Definitions of Study Variables

The key variables of interest in this study are demographic and clinical characteristics, patient-reported health and disability outcomes, and healthcare resource utilizations. Most variables will be measured at baseline (i.e. index), and at weeks 12 and 24 after the initiation of Adalimumab; healthcare resource utilization will be summarized over the 6 month post-index period.

3.5.1 *Outcome/Endpoint Variables - Scoring of PRO Questionnaires*

Health Assessment Questionnaire Disability Index (HAQ DI)

In the HAQ DI, each category contains four response options ranging from 0-3, where 0 = without any difficulty and 3 = unable to do. In any event, a patient must have a score for at least six of the eight categories (i.e. Dressing and grooming, arising,

eating, walking, hygiene, reach, grip, and activities). The HAQ DI's scoring conventions allow for the computation of two disability indices:

1. Standard HAQ DI (preferred and traditional scoring method; takes into account the use of aids/devices)

There are three steps:

- 1) Sum the 8 category scores by using the highest sub-category score from each category.
 - For example, there are three sub-category items in "Eating". A patient responds with a 1, 2, and 0, respectively; thus, the category score is 2.
- 2) Adjust for use of aids/devices and/or help from another person when indicated.
 - Adjust the score for a category by increasing a 0 or 1 to a 2.
 - If the patient's highest score is a 2, it would remain as 2.
- 3) Divide the summed category scores by the number of categories answered to obtain a HAQ DI score of 0-3 (3=worst functioning).

2. Alternative HAQ DI Score (without aids/devices)

There are two steps:

- 1) Sum the scores for each category, ignoring scoring for aids/devices
- 2) Divide by the number of categories answered (minimum 6 required). This yields a score of 0-3 (3=worst functioning).

Short Form (36) Health Survey (SF-36)

SF-36 scoring will be conducted by following these 7 steps in accordance to the developer's recommendations:

Step 1: Data entry

SF-36 scoring must ensure that the survey form is complete and the respondent's answers are unambiguous. If there are missing responses, using a scoring algorithm could derive scores across the eight SF-36 health domain scales for nearly all survey respondents. If there are multiple responses for a single item, the following rules are applied:

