 - Age at baseline
 - Age groups
 - Gender at birth
 - Marital status (married, unmarried)
 - Medical plan type
 - ✓ The type of healthcare plan each patient is enrolled in at baseline will be determined, including National/Public insurance, Private insurance, Employer benefits, and Other
- **Clinical characteristics**
 - Initial Diagnosis of Rheumatoid Arthritis (RA)
 - ✓ Year of initial diagnose
 - Initiation of Adalimumab
 - ✓ First time administration (DD/MM/YYYY)
 - ✓ Dosage of first injection (in mg)
 - Disease status of RA
 - ✓ Moderate (defined as Disease Activity Score in 28 Joints (DAS28) between 3.2 and 5.1)
 - ✓ Severe (DAS28>5.1)
 - Erythrocyte sedimentation rate (ESR) (in mm/hour)
 - C reactive protein (CRP) (in mg/L)
 - Disease Activity Score in 28 joints (DAS28)

To calculate the DAS28, the physician or specialist nurse will:

1. Count the number of swollen joints (out of the 28)
2. Count the number of tender joints (out of the 28)
3. Take blood to measure the erythrocyte sedimentation rate (ESR) or C reactive protein (CRP); the latest measurement in the medical records may also be used if a blood draw is not standard for that visit

4. Ask the patient to make a 'global assessment of health' which will be indicated by marking a 10 cm line between very good and very bad

The physician or specialist nurse will then mark each component score on the CRF and the DAS28 score if calculated (an online scoring calculator for the DAS28 can be found at <http://www.das-score.nl/das28/DAScalculators/dascalculators.html>).

The DAS28 will be scored using the following formula:

$$\text{DAS28} = 0.56 * \text{sqrt}(\text{tender28}) + 0.28 * \text{sqrt}(\text{swollen28}) + 0.70 * \ln(\text{ESR or CRP}) + 0.014 * (\text{Global assessment of Health})$$

DAS28 scores will be interpreted using the following categorization:

- ✓ Remission: DAS28 \leq 2.6
- ✓ Low Disease Activity: $2.6 < \text{DAS28} \leq 3.2$
- ✓ Moderate Disease Activity: $3.2 < \text{DAS28} \leq 5.1$
- ✓ High Disease Activity: DAS28 > 5.1

– comorbidities

- ✓ Myocardial infarction
- ✓ Congestive heart failure
- ✓ Peripheral vascular disease
- ✓ Cerebrovascular disease
- ✓ Dementia
- ✓ Chronic pulmonary disease
- ✓ Connective tissue disease
- ✓ Ulcer disease
- ✓ Mild liver disease
- ✓ Diabetes
- ✓ Hemiplegia
- ✓ Moderate or severe renal disease
- ✓ Diabetes with end-organ damage
- ✓ Any tumor
- ✓ Leukemia
- ✓ Lymphoma
- ✓ Moderate or severe liver disease
- ✓ Metastatic solid tumor
- ✓ AIDS

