5.2 Analysis Plan for Demographic and Clinical Characteristics

- Descriptive statistics will be presented for patient demographics (Excel Table 1), and clinical characteristics (Excel Table 2) for all patients. The following measures will be assessed as of the patient's baseline:
 - Patient age (mean, SD, minimum, maximum, median; categories: 18-34, 35-44, 45-54, 55-64, 65-74, 75+, missing)
 - Gender (male, female, missing)
 - Marital status (married, unmarried, missing)
 - Medical insurance type (National/Public insurance, Private insurance, Employer benefits, other, no insurance, missing)
 - Disease Activity Score in 28 joints - DAS28 (mean, SD, minimum, maximum, median; categories: Remission, Low Disease Activity, Moderate Disease Activity, High Disease Activity, Missing)
 - Number of patients with each of the comorbidities at baseline visit (See 3.5.2), and number of patients with any of these comorbidities

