6. LIST OF TABLES AND FIGURES IN EXCEL WORKBOOK

Results of the analysis for this study as outlined above will be summarized using MS Excel tables and will be presented as follows:

Excel Tables / Figures	Description
1	Demographic Characteristics at Baseline
2	Clinical Characteristics at Baseline
3.1	Change in HAQ DI at Weeks 12 and 24 after Initiation of Adalimumab
3.2	Change in HAQ DI at Weeks 24 after Initiation of Adalimumab - Observed VS Withdrawal Population
4	Change in SF-36 Domain Scales at Weeks 12 and 24 after Initiation of Adalimumab
5	Change in EQ-5D-3L Index at Weeks 12 and 24 after Initiation of Adalimumab
6	Change in WPAI at Weeks 12 and 24 after Initiation of Adalimumab
7	Change in Patient Satisfaction Questions at Weeks 12 and 24 after Initiation of Adalimumab
8	Patients' Global Impression of Change at Weeks 12 and 24 after Initiation of Adalimumab
9	Post-index Healthcare Resource Utilization - RA Related
10.1	Associations between Disease Severity and PROs
10.2	Associations between Change in Disease Severity and Change in PROs
11	GLM - Modifying Effects on Changes in PROs

Please see the document, "AbbVie_ROCKI_Tableshell_V0.2_15Jan2018_Taiwan.xlsx" for the full set of table shells.

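### DAS28 is scheduled at every assessment visit, but the SAP describes it only at baseline, so the clinical part of the stated 24-week follow-up step has no descriptive output

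*Protocol*

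**What the plan says.** Protocol 4.0 (Abstract) gives three steps towards the objective. The third is to follow patients who start adalimumab for 24 weeks and "identify the changes in clinical, economic, and PROs associated with adalimumab". Clinical change is named separately from patient-reported outcomes.

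Protocol 9.1.1, Table 1, schedules DAS28 (ESR or CRP version) at baseline, Week 12, Week 24 and early termination. Protocol 9.3 uses post-baseline DAS28 in one exploratory item: "Association between change in disease severity and change in PROs".

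SAP 3.5.2 defines remission, low, moderate and high activity ("DAS28 scores will be interpreted using the following categorization"). SAP 5.2 asks for the mean, SD, range and median of DAS28, with "categories: Remission, Low Disease Activity, Moderate Disease Activity, High Disease Activity, Missing", all as of baseline. SAP 6 lists the matching output, Table 2, as "Clinical Characteristics at Baseline". SAP 5.5 relates DAS28 to each PRO (Table 10.1, no visit stated) and DAS28 change to PRO change at Weeks 12 and 24 (Table 10.2), both by bivariate linear regression.

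**The concern.** A step that promises clinical change should lead to at least one output showing it. HAQ DI, SF-36, EQ-5D-3L and WPAI each have a table of change from baseline with a mean, SD and 95% CI. DAS28 is collected on the same schedule and has none.

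Two things would be lost. The HAQ DI change could not be read beside disease control in the same patients. Table 10.2 would also report a slope against a DAS28 change whose size and spread no planned table shows.

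The intended audience makes the gap more visible. The background in both documents describes a Taiwanese payer policy with DAS28 of 3.2 or below as one of its criteria. That policy applies after two years of biologic treatment, so 24-week data would not test it. A payer would still be likely to ask how many patients were at or below that level.

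**Working it through.** The plan gives no figure for DAS28 change or response, so there is none to reproduce. The check sets the passages side by side, with a short calculation on the two formulas.

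**1. Planned outputs.** SAP 6 lists 13 tables: 1, 2, 3.1, 3.2, 4, 5, 6, 7, 8, 9, 10.1, 10.2 and 11.

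| Use of DAS28 | Tables |
|---|---|
| Described (mean, categories) | 2, baseline only |
| Used as a variable in a regression on PROs | 10.1 (visit not stated), 10.2 (change at Weeks 12 and 24) |
| Level, change or categories described at Week 12 or 24 | none |

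Tables 3.1 and 11 also use severity, but only its baseline value, for adjustment or effect modification.

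**2. What Table 10.2 can show.** A bivariate slope gives the PRO change per unit of DAS28 change. The same slope is compatible with a large or a small average fall in DAS28, and with any number of patients in remission.

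**3. Other sources.** The disease-status item on the follow-up case report form (Protocol Appendix C) offers only moderate or severe. It cannot show low activity or remission.

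**4. Number of values.** The plan is for about 100 patients. With the SAP's 13% drop-out, 100 × (1 − 0.13) = 87. That gives 87 to 100 per visit, or 2 × 87 = 174 to 2 × 100 = 200 over two visits. This is a ceiling, because the form asks for the score only if it has been calculated.

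**5. Baseline categories and the formulas.** Entry requires DAS28 above 3.2 and the Low category ends at 3.2, so few or no patients should fall in Remission or Low at baseline. Zero is not guaranteed, because the formulas differ:

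- Protocol 9.2.4.7, CRP version: inflammation term 0.36 × ln(CRP), plus a constant 0.96.
- SAP 3.5.2, single formula: 0.70 × ln(ESR or CRP), no constant.
- SAP minus Protocol for a CRP-based score, other terms held equal: 0.34 × ln(CRP) − 0.96. This is negative when CRP < exp(0.96/0.34) ≈ 16.8 mg/L.

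An illustration with an assumed CRP of 5 mg/L: the Protocol gives 0.36 × 1.609 + 0.96 = 1.54 and the SAP gives 0.70 × 1.609 = 1.13, a difference of −0.41. A patient eligible at 3.40 under the Protocol scores 2.99 under the SAP, which is Low.

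**6. Consequence for change scores.** The constant cancels in a change, but the coefficient does not. The two formulas differ in change by 0.34 × [ln(CRP at follow-up) − ln(CRP at baseline)]. For an assumed fall from 5 to 1 mg/L this is 0.34 × (0 − 1.609) = −0.55, so the SAP formula would show a fall 0.55 points larger. The formula must therefore be settled before any DAS28 change is tabulated, and before Table 10.2 is run.

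**The case against.** The strongest reply is that DAS28 was never meant as an outcome. The three abstract steps serve an objective about quality of life and work productivity. DAS28 change is absent from Protocol 8.0, from the variable list in Protocol 9.3 except through the association item, and from the SAP objectives. Protocol 9.2.4.7 says the clinical form data, including DAS28, are for segmenting the population. SAP 3.5.2 lists DAS28 among exposure and independent variables. All of this stands, so a reader who infers that an endpoint was dropped would be wrong.

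A reader might also infer that clinical response goes unreported. That is too broad. HAQ DI responders, the global impression of change, RA surgeries, hospitalisations and RA medication are all reported after baseline, and Table 10.2 uses DAS28 change. What is missing is a description of DAS28 itself. HAQ DI and the global impression are patient-reported, so they do not answer a step that names clinical change separately.

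A third tempting reading is that the baseline Remission and Low rows are empty by design. The formula difference, entry on either the ESR or the CRP version, and entry deviations could all put patients there.

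Finally, general wording might cover the gap. Protocol 9.7.3 says "Descriptive analysis will be conducted on all key parameters", and SAP 3.5 says "Most variables will be measured at baseline (i.e. index), and at weeks 12 and 24 after the initiation of Adalimumab". The first does not name DAS28, the second concerns measurement, and no listed table follows from either for DAS28. The workbook of table shells might show more and was not available. SAP 5.1 lets tables be modified in light of the results, but a DAS28 table added at that stage would be open to a charge of selective reporting.

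**Conclusion.** The point holds in a limited form. As written, the SAP describes DAS28 at baseline only and leaves the clinical part of abstract step 3 without a descriptive answer. The size is two scheduled visits with at most about 87 to 100 scores each. No listed endpoint is lost, and the primary HAQ DI analysis is unaffected.

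The conclusion rests on three things: reading clinical change in step 3 as including disease activity, for which DAS28 is the only scheduled score; the SAP text and table list, without the shell workbook; and the planned 100 patients with the SAP's drop-out rate. The number of usable scores could be lower, and the documents give no basis for estimating it.

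**What to change.** 1. Reconcile the DAS28 formulas in Protocol 9.2.4.7 and SAP 3.5.2, including the unit of the global assessment, which the Protocol formula gives as cm and the SAP formula leaves unstated. State that each patient is scored with the same version (ESR or CRP) at all visits.

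2. Add one table to SAP 5.5 and to the list in SAP 6, labelled descriptive or exploratory, in the same population as Table 3.1. For Weeks 12 and 24 it should give mean DAS28, mean change from baseline with 95% CI, category n (%) or shift from baseline, and the number missing. It belongs in 5.5, not 5.4, because DAS28 change is not a secondary endpoint.

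3. Specify this before the results are seen.

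The cost is one extra table. Table 10.2 already requires DAS28 change at both visits, so the derivation is planned and no new visit is needed. The drawback is that n may fall below 87 to 100 per visit. The form pages as reproduced show no field for the patient's global assessment (figures are missing from the text), so an uncalculated or differently calculated score may not be recoverable from the form alone. Reporting the number missing makes that visible.
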